13.4 Biochemical markers of bone turnover (A011203-ST3)

For each of the biomarkers of bone formation (namely, bone-specific alkaline phosphatase, osteocalcin, P1NP) and bone resorption (namely, CTX-1, Trap5b and bone sialoprotein) the percent change after 2 cycles of treatment from pre-treatment levels will be determined.

A two sided $\alpha=0.01$ z-test will be used to assess whether the percent change in a given bone absorption biomarker differs with respect to treatment.

Assuming the variability in percent change in a given bone absorption biomarker is similar between the treatment arms and at least 32 or more patients on each treatment arm have both a pre and Week 8 biomarker determination, then a two sided $\alpha=0.01$ z-test will have a 90% chance of detecting whether the mean difference between the percent change in the biomarker of those treated with Z-Endoxifen HCl and that of those treated with tamoxifen is at least 1 standard deviation or more.

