13.1.3 Sample Size, Accrual Time and Study Duration

This trial was designed under the assumption that the median progression-free survival time among patients receiving tamoxifen is 3.0 months. Disease assessments in this trial are made at a frequency that is half the hypothesized median of the tamoxifen arm. Stone et al [41, 42] (2, 3) found that when disease assessments are made at a frequency that is half the control median, the difference in power between the log-rank test (with documented progression times) and generalized log-test with interval censored data was < 3%. As such we will determine the sample size assuming a log-rank test will be used with one-sided alpha=0.10 and power=95% so that the interval censored approach with the generalized log-rank test will have a power of > 90%.

With a sample size of 80 eligible patients (40 per treatment arm randomized in equal numbers) over a 15 month period and followed at least another 9 months after the close of enrollment before analysis is undertaken, a one-sided alpha=0.10 generalized log-rank test will have at least a 90% chance of detecting a 50% decrease in hazard of disease progression with Z-Endoxifen HCl relative to tamoxifen.

That corresponds to being able to detect an increase in the median PFS time from 3.0 months with tamoxifen to 6.0 months with Z-Endoxifen HCl.

An additional 14 patients will be screened to account for ineligible patients (tumors that are ER negative on biopsy) and those who cancel participation prior to starting treatment.

As of November 1, 2016, 24 (30%) of the 81 patients enrolled on this trial were found to have ER negative and/or HER2 positive breast cancer, a second primary cancer, or benign disease, making them ineligible. Therefore, the number of patients needed to be screened to obtain 80 eligible patients will be increased from 94 to 115 patients.

The efficacy analysis will be conducted when at least 72 patients have provided documentation of local, regional or distant disease progression or death without progression of disease.

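### Section 13.4 compares arms on unadjusted percent change in each bone resorption marker; a baseline-adjusted log-scale model would be more precise at no data cost, although the stated power is correct

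*Combined protocol and SAP*

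**What the plan says.** Section 13.4 lists three formation markers and three resorption markers. For each of the six, "the percent change after 2 cycles of treatment from pre-treatment levels will be determined". A between-arm test is named only for the resorption markers: at two-sided 0.01, a "z-test will be used to assess whether the percent change in a given bone absorption biomarker differs with respect to treatment".

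The power statement begins "Assuming the variability in percent change in a given bone absorption biomarker is similar between the treatment arms" and requires that "at least 32 or more patients on each treatment arm have both a pre and Week 8 biomarker determination". It then claims 90% power when the difference in mean percent change "is at least 1 standard deviation or more". No numerical SD is given.

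Section 13.4 mentions no transformation, baseline covariate or adjustment for the stratification factors. Section 14.3 describes assays and sampling and adds no analysis model. The pre-treatment sample is scheduled for Cycle 1, Day 1 (sections 6.2.5 and 14.3.3).

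**The concern.** Percent change has the baseline in its denominator. It cannot fall below −100% but has no upper bound, so low baselines can produce very large values. It also tends to be negatively related to baseline. On the log scale, with equal SDs at the two visits and correlation ρ, change correlates with baseline at −√((1−ρ)/2), which is −0.50 at ρ = 0.5 and −0.32 at ρ = 0.8. In arms of about 32, a chance baseline imbalance therefore enters an unadjusted contrast.

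The trial admits both measurable and bone-only disease and stratifies on this (sections 3.3.1 and 4.8). It is reasonable to expect bone-marker baselines to differ between such patients, but that is an inference and not a figure in the documents.

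The stake is precision in the one correlative comparison that has a stated alpha and power. Sections 13.2.3 and 13.5 call their analyses exploratory, and section 13.3.2 is tabulation and estimation.

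**Working it through.** **Inputs from the plan.** Two-sided α = 0.01; difference 1 SD; n = 32 per arm with paired samples; 1:1 allocation. The trial has 40 per arm (section 13.1.3), so 32 means 32/40 = 80% with paired samples.

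**Inputs assumed.** Correlation ρ between log baseline and log follow-up of 0.5 to 0.8, and equal log-scale SDs at the two visits. The documents give neither.

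**Step 1: the plan's own figure.**
- Normal approximation: power = Φ(√(n/2) − 2.576) = Φ(4 − 2.576) = 92.3%. The n for 90% is 2(2.576 + 1.282)² = 29.8, so 30 per arm.
- Noncentral t, 62 df, noncentrality 4: 90.6% at 32 per arm and 89.5% at 31. So 32 is the smallest n that reaches 90% with a t-test, and the plan's claim reproduces.
- Using the critical value 2.576 with 62 df gives a true two-sided error of about 0.012 under normality, not 0.010.

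**Step 2: variance after adjustment.** With equal SDs σ, an unadjusted log change has variance 2(1−ρ)σ². The residual after regression on log baseline has variance (1−ρ²)σ². The ratio is (1−ρ²)/(2(1−ρ)) = (1+ρ)/2.

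**Step 3: power on one scale, with a t reference.** The effect is 1 SD of log change. Noncentrality is 4/√((1+ρ)/2), with 61 df.

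| ρ | Variance ratio | Noncentrality | Power, 32 per arm |
|---|---|---|---|
| unadjusted log change | 1 | 4.00 | 90.6% |
| 0.5 | 0.75 | 4.62 | 97.2% |
| 0.6 | 0.80 | 4.47 | 96.2% |
| 0.7 | 0.85 | 4.34 | 95.0% |
| 0.8 | 0.90 | 4.22 | 93.6% |

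Estimating the baseline slope multiplies the variance by about 1 + 1/(2n−4) = 1 + 1/60, which takes 0.2 to 0.4 points off the adjusted rows.

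**Step 4: unequal SDs.** If the follow-up SD is k times the baseline SD, the variance ratio is k²(1−ρ²)/(1 + k² − 2ρk). At k = 1.2:
- ρ = 0.7: 1.44 × 0.51/0.76 = 0.966, a 3% reduction.
- ρ = 0.8: 1.44 × 0.36/0.52 = 0.997, a 0.3% reduction.

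If the follow-up SD is below the baseline SD, the gain is larger. At k = 0.8 and ρ = 0.7, 0.64 × 0.51/0.52 = 0.63.

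**Step 5: the planned test itself.** Steps 2 to 4 use log change as comparator, whereas the plan uses raw percent change. A simulation covers that comparison: lognormal marker, equal log-SDs of 0.3, 0.5 or 0.7, ρ of 0.5, 0.7 or 0.8, 32 per arm, 4,000 runs per setting, and a reduction equal to 1 SD of percent change. The percent-change z-test had power 91.8% to 96.4%, and log-scale ANCOVA with a t reference 93.9% to 99.9%. ANCOVA was higher in all nine settings, by about 2 to 5 points. Null rejection was about 0.009 to 0.014 for both.

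**The case against.** The strongest reply is that nothing here is an error. Under randomisation, a between-arm comparison of percent change is unbiased and easy to interpret, its simulated error rate is close to nominal, and its power already meets the target. The substudy is optional, no trial decision depends on it, and the objectives in sections 2.3.3 and 14.3.2 are framed within each treatment, where percent change is a natural summary. No document gives a distribution, SD or correlation for any marker, so skewness and the size of the gain are assumed. All of this stands. It limits the point to an efficiency improvement but does not remove it, because the better analysis uses data already collected.

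Three stronger readings should be resisted:
- A reader might infer that the 90% power claim is wrong. It reproduces.
- A reader might infer that all six markers are compared this way. The z-test is named only for resorption markers; for formation markers the percent change is only to be calculated.
- A reader might set the z-based 92.3% for 1 SD of percent change beside normal-approximation figures of 95.0% to 98.0% for ANCOVA on log change. That mixes two outcome scales and uses a normal critical value where the proposed model uses t. The like-for-like figures are those in the table.

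**Conclusion.** The point holds as a minor, free improvement limited to the resorption markers. With equal log-scale SDs and ρ of 0.5 to 0.8, adjustment cuts variance by 25% to 10% relative to unadjusted log change and raises t-based power at 32 per arm from 90.6% to between 97.2% and 93.6%. Against the planned percent-change z-test, the simulated gain is about 2 to 5 points. These figures are conditional: with a follow-up SD 1.2 times baseline and ρ near 0.8, the gain over log change is close to nil.

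The adjustment is worth more if paired samples fall short, which is possible because patients may decline the substudy (section 4.7.1). With 26 per arm, the t-based formula of step 3 (noncentrality √13 = 3.61 unadjusted, divided by √((1+ρ)/2) when adjusted) gives 81.8% unadjusted and 92.6% to 86.3% adjusted for ρ of 0.5 to 0.8.

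The documents do not support calling the planned test invalid or underpowered.

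**What to change.** In section 13.4, for each resorption marker, specify linear regression of the log marker at the planned post-baseline visit on treatment arm and log baseline, with a t reference distribution. Report the adjusted ratio of geometric means with its confidence interval, and keep percent change as a descriptive summary. This changes the reported quantity from a difference in mean percent change to a ratio, so the power statement should name the scale on which its 1 SD is defined.

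Reconcile the visit in the same edit. Section 13.4 refers both to 2 cycles (2 × 21 days = 6 weeks) and to Week 8, while objective 2.3.3 refers to 12 weeks (4 cycles). The scheduled on-treatment samples are at the end of cycles 2 and 8 and at progression, so none is planned specifically for Week 8 or Week 12.

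The cost is SAP wording only, with no new samples, visits or patients.

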3.3 Registration Eligibility Criteria

Registration must be completed within 28 days of Pre-registration

3.3.1 Patients with either measurable disease as defined by RECIST criteria (See Section 11.0) or bone only disease are eligible. Note: Those patients with both non-measurable disease and bone metastases are eligible.

- Non-measurable bone only disease: Non-measurable bone only disease may include any of the following: blastic bone lesions, lytic bone lesions without a measurable soft-tissue component, or mixed lytic-blastic bone lesions without a measurable soft-tissue component.
- Lytic bone lesions, with an identifiable soft tissue component, evaluated by CT or MRI, can be considered as measurable lesions if the soft tissue component otherwise meets the definition of measurability previously described.

3.3.2 No tumors involving spinal cord or heart.

3.3.3 No visceral crisis, lymphangitic spread or known brain metastases: Visceral crisis is not the mere presence of visceral metastases, but implies severe organ dysfunction as assessed by symptoms and signs, laboratory studies, and rapid progression of disease.

3.3.4 Histologic confirmation, from the A011203 Pre-registration biopsy, by institutional/local pathologist of either locally advanced or metastatic breast cancer that is estrogen receptor positive and HER2 negative.

Those patients with bone only disease with either no tumor or insufficient tumor for ER/PR and HER2 staining after the bone biopsy are still eligible to participate in this study.

3.3.5 Estrogen receptor positive disease is defined as > 10% nuclear staining.

3.3.6 **HER2 Negative Disease as per 2013 ASCO/CAP guidelines, one of the following must apply:**

- 1) 0 or 1+ by IHC and not amplified by ISH
- 2) 0 or 1+ by IHC and ISH not done
- 3) 2+ by IHC and not amplified by ISH or
- 4) IHC not done and not amplified by ISH

3.3.7 **None of the following therapies are allowed prior to registration*:**

- Chemotherapy \leq 2 weeks
- Immunotherapy \leq 2 weeks
- Biologic therapy \leq 2 weeks
- Hormonal therapy \leq 2 weeks
- Monoclonal antibodies \leq 2 weeks
- Radiation therapy \leq 2 weeks
- Anti-Her-2 or other “targeted” (e.g. mTOR) therapy \leq 2 weeks

*Note: Any toxicities derived from these therapies must be \leq grade 2 prior to starting study therapy.

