8.1.4 Full supportive care

Patients should receive full supportive care while on this study. This includes blood product support, antibiotic treatment and treatment of other newly diagnosed or concurrent medical conditions and concomitant medications such as anti-diarrheals, analgesics and anti-emetics. All blood products and concomitant medications received from Cycle 1 Day 1 of study drug until 30 days after the final dose are to be recorded in the medical record.

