14.3 Biochemical markers of bone turnover (Alliance A011203-ST3)

14.3.1 Background

In postmenopausal women, tamoxifen is known to increase bone mineral density and reduce the risk of fracture. Data from our group have now demonstrated that treatment of ovariectomized mice with an anti-cancer dose of endoxifen (50 mg/kg/day) results in substantial increases in bone mineral density and bone mineral content throughout the skeleton [57]. Additionally, we have demonstrated that a moderate dose of endoxifen (10 mg/kg/day) has similar effects in a pre-clinical ovariectomized rat model. Interestingly, this same dose of endoxifen resulted in increased bone mass in intact rats (unpublished data), an effect opposite of that reported for other selective estrogen receptor modulators including tamoxifen and raloxifene. In order to obtain data with regard to the effects of endoxifen on bone, and to directly compare this to the known effects of tamoxifen, we will assess serum procollagen type 1 amino-terminal propeptide (PINP, a bone formation marker) and C-Telopeptide of Type I Collagen (CTX-1, a bone resorption marker) at baseline, following 6 weeks of treatment and following 6 months of treatment. Samples will be drawn fasting in the AM and the assays will be conducted using validated ELISAs in [name] laboratory.

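### The bone-marker comparison in Section 13.4 pools patients with and without bone metastases, so a difference between arms would not by itself show an effect on the skeleton

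*Combined protocol and SAP*

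**What the plan says.** Section 14.3.1 states the aim of ST3 as "to obtain data with regard to the effects of endoxifen on bone" and as a direct comparison with the known effects of tamoxifen. The argument there rests on bone mineral density, fracture risk and ovariectomized animals. Tumor in bone is not mentioned.

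Section 13.4 takes percent change from pre-treatment after 2 cycles in three formation and three resorption markers. The planned test is a z-test at two-sided 0.01, which "will be used to assess whether the percent change in a given bone absorption biomarker differs with respect to treatment". The power statement begins "Assuming the variability in percent change in a given bone absorption biomarker is similar between the treatment arms" and requires 32 patients per arm with paired samples. It concludes that the "z-test will have a 90% chance of detecting whether the mean difference" in percent change between arms when that difference "is at least 1 standard deviation or more".

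Section 3.3.1 admits patients with measurable disease "or bone only disease are eligible", and also those with both non-measurable disease and bone metastases. Section 4.7.1 requires the substudies to be offered to all patients. Section 4.8 balances randomization on measurable versus bone-only disease.

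Sections 6.2.5, 13.4 and 14.3 contain no stratum, covariate, subgroup or sensitivity analysis for bone metastases or for bone-active drugs.

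**The concern.** Serum markers of bone formation and resorption measure bone made and broken down anywhere in the body. Section 3.3.1 describes the eligible bone lesions as lytic, blastic or mixed, and Section 11.4.5 allows that apparently new lesions may be healing or flare of existing ones. In a patient with bone metastases, a marker change therefore mixes skeletal remodeling with what the treatment does to the tumor.

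Section 13.1 hypothesizes greater antitumor activity with Z-Endoxifen HCl. If that is true, and it extends to bone lesions, resorption markers could fall further in that arm with no difference between the drugs in their effect on the skeleton. Section 13.4 would show a difference and offer no means of attributing it. At stake is the reading of a correlative result that ST3 was set up to obtain.

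**Working it through.** **1. The plan's own figure.** Inputs from Section 13.4: two-sided alpha 0.01, difference of 1 SD, 32 per arm.
- z-test: power = Φ(√(32/2) × 1 − 2.576) = Φ(4 − 2.576) = 92.3%.
- Two-sample t-test with 62 degrees of freedom: 90.6%.
- Sample size by z for 90%: 2 × (2.576 + 1.282)² = 29.8, so 30 per arm against the plan's 32.

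The stated 90% stands.

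**2. What the pooled difference estimates.** Let f be the share of patients with bone metastases, S the skeletal difference between arms and T the extra tumor-driven difference in patients who have them, both in SD units. The pooled mean difference is S + f × T. The test addresses whether this sum is zero. It does not identify S.

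**3. How often T alone would give a positive result.** The documents give neither f nor T. Assume S = 0, T = 1 SD, f = 30%, 50% or 70%, and a common SD. Rejection probability = Φ(4f − 2.576), against a nominal 1%:

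| f | Pooled difference (SD) | Rejection probability |
|---|---|---|
| 30% | 0.3 | Φ(−1.376) = 8% |
| 50% | 0.5 | Φ(−0.576) = 28% |
| 70% | 0.7 | Φ(0.224) = 59% |

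A mixture of shifted and unshifted patients in one arm also raises the average variance to 1 + f(1 − f)/2. That gives SDs of 1.05, 1.06 and 1.05 and rejection in 8%, 25% and 53%. With T = 0.5 SD and the common SD, the figures are 2%, 6% and 12%. These are not type I errors for the total effect, which really differs in this scenario. They are the chance of a positive test that says nothing about the skeleton.

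**4. What randomization covers.** It balances baseline bone disease and baseline co-medication in expectation. It cannot balance tumor response, which is an outcome of treatment. The factor in Section 4.8 does not pick out bone metastases among patients with measurable disease, and Section 13.4 does not use it.

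**5. What the stratum without bone metastases can deliver.** With n = 32(1 − f) per arm, power for 1 SD = Φ(√(n/2) − 2.576), and the 99% interval half-width = 2.576 × √(2/n):

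| f | n per arm | Power | Half-width (SD) |
|---|---|---|---|
| 0 (pooled) | 32 | 92% | 0.64 |
| 30% | 22.4 | 78% | 0.77 |
| 50% | 16 | 60% | 0.91 |
| 70% | 9.6 | 35% | 1.18 |

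**The case against.** The strongest reply is that nothing in Section 13.4 is wrong as a test. Randomization, with disease type as a balancing factor, makes the arm comparison valid for the total effect on the marker. The stated objectives (Sections 2.3.3 and 14.3.2) speak only of marker changes, and no text says that a bone-protective effect will be declared. ST3 is optional and correlative. All of this stands, and it limits the point to interpretation. It does not remove the point, because Section 14.3.1 wants an effect on bone argued in skeletal terms, and the planned analysis cannot supply one.

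A reader might also infer that metastases, by widening the SD, undermine the stated 90% power. The documents do not support that. The power is for 1 SD of the patients analyzed, so a wider SD leaves it unchanged. A loss appears only if that SD is replaced by the SD of patients without bone disease, which the plan never uses. Even then, restricting to those patients is no general remedy. Assume f of 30%, 50% or 70% and an SD in patients with bone metastases 1.5 or 2 times that of the others. The pooled SD is √(f k² + 1 − f), where k is that ratio. Pooled power for one unaffected-patient SD is then 80% or 63%, 71% or 48%, and 63% or 38%. The stratum's 78%, 60% and 35% are lower in four of these six cases.

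A reader might finally infer that bone-active drugs bias the comparison and go unrecorded for analysis. Baseline use is balanced in expectation and mainly adds noise or dilution. Only use that starts or changes after randomization could differ by arm, and the documents give no reason to expect that it will. Section 8.1.4 names the medical record as the place where "concomitant medications received from Cycle 1 Day 1 of study drug until 30 days after the final dose are to be recorded". It does not say only there, and the case report forms are not part of the documents. What remains is that Section 13.4 does not address these drugs.

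**Conclusion.** The concern holds as a limit on what ST3 can conclude. The pooled test is a valid, correctly powered test of the total effect on a marker. A positive result would not by itself show a skeletal effect, because tumor response in bone metastases could produce it. Under the assumed 30% to 70% bone involvement and a 1 SD tumor-driven difference, that would happen in about 8% to 59% of trials with no skeletal difference at all. The share and the size of the difference are both assumptions, so the range shows sensitivity and is not a forecast. The stated power needs no correction, co-medication is a secondary point, and the primary PFS analysis is untouched.

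**What to change.** In Section 13.4:

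- Stratify, or adjust, the arm comparison by bone metastasis at baseline (yes or no), taken from the baseline imaging. The study calendars in Sections 5.1 and 5.2 schedule a bone scan or PET-CT in the pre-registration period. Section 11.4.2 has non-measurable sites, which under Section 11.2.2 include bone lesions, recorded at baseline.
- Report the arm difference with a confidence interval in each stratum.
- Keep the pooled test, labeled as the total effect on the marker.
- State that a skeletal effect will be claimed only if the estimate in patients without bone metastases supports it.

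As a secondary step, capture starts of, or changes in, bone-active drugs between baseline and the end of cycle 2, if no study form already does so. Use this in a sensitivity analysis only, since such changes occur after randomization.

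The cost is a few lines of analysis text and possibly one form item. The real price is precision: the stratum that carries the skeletal conclusion is small, so its result should be presented as an estimate with a wide interval and not as a powered test.

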13.5 Z-Endoxifen HCl and Tamoxifen Pharmacokinetics and Pharmacogenetics (A011203-PP)

The pharmacokinetic, pharmacogenetic and pharmacodynamic data will be examined in an exploratory and hypothesis-generating fashion. A population PK will be developed using the software program NONMEM®, Version 7 (ICON Development Solutions, [name], USA). The model will be parameterized in terms of AUC (the primary endpoint), as well as clearance and volume of distribution. Criteria for model selection will include the likelihood ratio test, shrinkage estimates, reasonableness of parameter estimates, as well as goodness-of-fit plots. Attempts will be made to identify the covariates that affect drug behavior or those that explain variability in this patient population.

The primary pharmacokinetic endpoint for exploring relationships with efficacy/adverse effects will be endoxifen AUC. Pharmacokinetic-Pharmacodynamic relationships will be explored for effects of endoxifen on efficacy-related, adverse events or laboratory parameters of clinical interest. Exploratory/graphical analyses will be conducted for PK/PD evaluations and may be followed by model-based analyses. The data may be pooled with data from other/future studies for additional population PK/PD analyses.

